### 4.2. General Statistical Methods and Data Handling

#### 4.2.1. General Methods

All output will be incorporated into Portable Document Format (PDF) or Word files, sorted and labeled according to the International Conference on Harmonisation (ICH) recommendations, and formatted to the appropriate page size(s).

A list of tables, figures and listings to be generated, as well as mock shells, are provided in a separate document.

Tabulations will be produced for appropriate demographic, baseline, efficacy and safety parameters. Each table will present all patients combined, regardless of number of doses, unless otherwise specified.

For categorical variables, summary tabulations of the number and percentage within each category (with a category for missing data) of the parameter will be presented.

For continuous variables, the number of non-missing values (n), the mean, median, standard deviation (SD), confidence intervals (CI), minimum and maximum will be presented. Additional statistics may be presented for certain endpoints as described in the sections below.

Time to event data will be summarized using Kaplan-Meier Methodology using 25th, 50th (median), and 75th percentiles with associated 2-sided 95% confidence intervals, as well as percent of censored observations.

If performed, all statistical tests will be two-sided and a difference resulting in a p-value of less than or equal to 0.05 will be described as statistically significant and potentially informative.

All collected data will be presented in patient listings.

The sections below describe the intended analysis of the endpoints. Additional sensitivity analysis may be employed in the event of any unforeseen data anomalies or data issues not known at the time of writing this analysis plan.

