#### 4.9.1.1. Descriptive statistics, all patients

Descriptive statistics will be presented for the following groups. Each group will be displayed as a different column in the same table, in this order:

1. Patients receiving the second dose at Week 12
2. Patients receiving the second dose at Week 16
3. Patients receiving the second dose at Week 20
4. Patients receiving the second dose at Week 24
5. Patients receiving only one dose
6. All patients, first dose – all patients through patient discontinuation, study completion (through Week 12 or Week 24), or until the second dose is received (whichever happens sooner)

Descriptive statistics (number of observations, unadjusted mean, SD, median, minimum and maximum) will be presented for WOMAC A, WOMAC B, WOMAC C and WOMAC total by visit (baseline through Week 52). Change from baseline will also be presented. For the change from baseline calculation, baseline is the WOMAC result obtained on Day 1 prior to first dose.

The adjusted change from baseline will also be presented. This will be done using a longitudinal mixed effects model for repeat measures (MMRM) with fixed effects for study time point, study site and baseline score. Patient will be the random effect. The analysis will include all study visits of data. This model assumes that missing values are missing at random. This model will be run separately for each group and for WOMAC A, WOMAC B, WOMAC C and WOMAC total.

This model will be run using the SAS/STAT® PROC MIXED procedure with an unstructured correlation matrix to model the within-subject errors. If the unstructured covariance matrix does not converge when fitting the mixed model, further investigation into the most appropriate correlation matrix will be conducted. The final selection of the correlation matrix to be used in fitting the mixed model will be fully documented in the results section of the CSR.

This model will provide the baseline adjusted Least Square Means (LSM) at each visit with the corresponding standard error (SE) and associated 95% CI.

Sample SAS code that can be used to implement the mixed effects analysis is provided below:

```
proc mixed data=dsin1 method=reml;  
  by group;  
  class subjid group avisitn siteid;  
  model chg= base group avisitn siteid;  
  repeated avisitn /type=un subject=subjid;  
  lsmeans group/diff=control ('1') cl;  
run;
```

In the above code, "group" refers to the groups listed below. The model will be run for each group separately.

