#### 4.9.1.2. Change from baseline, patients receiving two doses

##### Change from Baseline to Week 12

A within patient analysis will be completed for patients who receive two doses of FX006. Change in WOMAC A, WOMAC B, WOMAC C and WOMAC total from first dose (Day 1) to Week 12 will be compared to change in WOMAC from second dose to 12 weeks after the second dose using a paired t-test.

The paired t-test will be completed by using the SAS/STAT® PROC MIXED procedure. Using the PROC MIXED procedure allows for multivariate modelling. Model covariates are study site, baseline WOMAC score, and potentially other covariates. Baseline WOMAC score for the first dose comes from the baseline visit. Baseline WOMAC score for the second dose comes from the second dose visit.

Descriptive statistics will include number of observations, unadjusted mean, standard deviation, median, minimum and maximum. Change from baseline LSM, SE and 95% CI from the mixed model will also be presented. The difference between the first dose (the control) and the second dose will be presented, and estimated via LSM from the analysis model along with 95% confidence intervals and associated 2-sided p-values. This model assumes that missing values are missing at random. Only patients that have data for both time points (i.e., change from Day 1 to Week 12 and change from the second dose to 12 weeks after the second dose) will be included in the model.

All patients who receive two doses of FX006 will be combined in the analysis and results will be displayed in the same table.

Sample SAS code that can be used to implement the analysis is provided below:

```
proc mixed data=<ADaM> method=type3;
  class subjID site arm;
  model chg = base site arm/ alpha=0.05 ddfm=kr outp=pred residual solution;
  random subjID;
  lsmeans arm / diff cl alpha=0.05;
  ods output diff=diff1 lsmeans=lsml;
run;
quit;
```

In the above code, "arm" refers to the first or second dose administered (coded as a 1 or 2).

The analysis above will also be performed to compare the changes in WOMAC A, WOMAC B, WOMAC C and WOMAC total from first dose (Day 1) to Week 12 to the changes from first dose (Day 1) to 12 weeks after the second dose.

#### Change from Baseline to Week 4, 8 and 12

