##### Comparison of change from baseline to Week 12 for the first and second doses

AUE for WOMAC A, WOMAC B, WOMAC C and WOMAC total change from baseline for the first dose from Week 4 Week 12 will be compared to AUE for WOMAC A, WOMAC B, WOMAC C and WOMAC total for the change from baseline for the second dose from 4 to 12 weeks after the second dose using a paired t-test. The examination of WOMAC A (Pain) will be an indication of the durability of the pain relief response, where WOMAC B (Stiffness) and WOMAC C (Function) will provide an indication of the durability of the responses for these two sub-scales over the course of two doses.

The paired t-test will be completed by using the SAS/STAT® PROC MIXED procedure. Model covariates are study site, baseline WOMAC score, and potentially other covariates. Baseline WOMAC score for the first dose comes from the first dose visit. Baseline WOMAC score for the second dose comes from the second dose visit. Sample SAS code provided in section 4.9.1.2 will be used.

Descriptive statistics will include the LSM and standard error, 95% confidence interval, LSM difference from control (first dose Week 4 to Week 12), and 2-sided p-value. This model assumes missing at random and only includes observed data; missing data are not imputed in

this model. Only patients that have data for both time points (i.e., first dose Week 4 to Week 12 and second dose Week 4 to Week 12) will be included in the model.

All patients who receive two doses of FX006 will be combined in the analysis and results will be displayed in the same column.

The analysis above will also be performed where baseline for the second dose is defined as the baseline/Day 1 assessment prior to administration of the first dose of study treatment.

Comparison of change from baseline to second dose and change from second dose to comparable period after second dose

AUE for WOMAC A, WOMAC B, WOMAC C and WOMAC total change from baseline for the first dose from Week 4 to the second dose will be compared to the AUE for WOMAC A, WOMAC B, WOMAC C and WOMAC total change from baseline for the second dose from 4 weeks after the second dose to the comparable period after the second dose using a paired t-test.

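### SAP 4.9.1.2 calls its first-versus-second-dose comparison a paired t-test, but the printed code usually gives standard errors that are too small

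*SAP*

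**What the plan says.** In SAP 4.9.1.2, for patients given two doses, the 12-week change that follows the initial injection "will be compared to change in WOMAC from second dose to 12 weeks after the second dose using a paired t-test". Sample code offered for it starts "proc mixed data=<ADaM> method=type3", then has "model chg = base site arm/ alpha=0.05 ddfm=kr outp=pred residual solution" and "random subjID". The covariate `base` is the Day 1 score in the first-dose row. For the other row, "Baseline WOMAC score for the second dose comes from the second dose visit". Only patients with both changes enter the model, and the LSM difference, its 95% CI and a two-sided p-value are reported.

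The same code serves the AUE comparisons in SAP 4.9.1.4 ("Sample SAS code provided in section 4.9.1.2 will be used"), and SAP 4.9.2 analyses KOOS QOL in the same way. SAP 4.2.1 says "all statistical tests will be two-sided and a difference resulting in a p-value of less than or equal to 0.05" is to be called significant. SAP 4.9.1.1, by contrast, uses "repeated avisitn /type=un subject=subjid" with REML.

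SAP 4.9.1.2 also plans a version in which both changes are taken from Day 1. It does not say which score is then the covariate in the second row.

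**The concern.** A paired t-test takes its error variance from the spread of each patient's own difference between doses. The printed model takes it from a within-patient regression on `base`, which is possible only because `base` differs between the two rows. For a patient re-dosed at Week 12, one score is the first-dose outcome, is subtracted from the second-dose outcome, and is the second-dose covariate. That regression then explains much of the spread, and the explained part is lost from the standard error.

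Confidence intervals would be too narrow, and results would be called significant too often, on the question of whether the second dose works as well as the first. This applies to WOMAC A, B, C and total, to KOOS QOL, and to the AUE runs that use the second-dose-visit score as covariate.

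**Working it through.** **Inputs from the documents.** SAP 4.1: 200 × 0.66 × 0.75 = 99, which reproduces the planned 100 or so completers. SAP 5: more than 90% were re-dosed, so at least about 180 of 200, and 180 × 0.75 = 135 at the planned completion rate. Simulations used 100-180 pairs, the roughly 20 centres of the protocol synopsis, and two-sided 0.05. Re-dosing may occur at Week 12, 16, 20 or 24.

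**Assumed, because the documents are silent.** Between-visit correlation (0.2-0.8), SD (0.7 on the 0-4 scale), drug-effect curve, and share re-dosed at Week 12.

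**Mechanism.** For each patient let D = second change − first change, and B = second `base` − first `base`. Site cancels. At slope b the dose contrast is mean(D) − b·mean(B), with variance about var(D − bB)/n, and

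var(D − bB) = var(D − b_W·B) + (b_W − b)²·var(B),

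where b_W is the within-patient slope. Type 3 estimates only the first term. The GLS contrast uses b pulled toward the between-patient slope b_B, so the second term is missing from the standard error.

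**Hand calculation: all re-dosed at Week 12** (unit variances, equal means, exchangeable correlation 0.5, large sample).
- D = Y24 − 2·Y12 + Y0 and B = Y12 − Y0. So var(D) = 6 × 0.5 = 3, var(B) = 2 × 0.5 = 1, cov(D,B) = −3 × 0.5 = −1.5.
- b_W = −1.5. var(D − b_W·B) = 3 − 1.5² × 1 = 0.75, so the residual variance is 0.375.
- Sum of changes S = Y24 − Y0, variance 1. Sum of baselines T = Y0 + Y12, variance 3. cov(S,T) = −0.5, so b_B = −0.5/3 = −0.167.
- Slope ignoring patients: (−1.5 − 0.5)/(1 + 3) = −0.5. Patient mean square: (3 + 1)/2 − 0.5² × (1 + 3)/2 − 0.375 = 1.125. Patient variance: (1.125 − 0.375)/2 = 0.375, which is positive.
- Weights: within 0.5/0.375 = 1.33, between 1.5/1.125 = 1.33. GLS slope = −(1.5 + 0.167)/2 = −0.833.
- Missing term: (1.5 − 0.833)² × 1 = 0.444. SE ratio = √(0.75/1.194) = 0.79. Rejection = P(|Z| > 1.96 × 0.79) = 12%.

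**Same, nobody re-dosed at Week 12** (four distinct scores). var(D) = 2, var(B) = 1, cov(D,B) = −1, so b_W = −1 and var(D − b_W·B) = 1. b_B = −1/3, the weights are 1 and 1.5, and the GLS slope is −(1 + 0.5)/2.5 = −0.6. Missing term: 0.4² × 1 = 0.16. SE ratio = √(1/1.16) = 0.93, and rejection is about 7%. The shared score enlarges the error but is not its only source.

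**Simulation of the printed model** (Kenward-Roger or t reference, no dose difference):

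| Setting | SE / true SD | Rejection |
|---|---|---|
| All re-dosed at Week 12, correlation 0.2 / 0.4 / 0.6 / 0.8 | 0.87 at 0.4, 0.79 at 0.6 | 7.8 / 9.2-9.4 / 11.5-12.2 / 19.2% |
| None at Week 12, correlation 0.2-0.7 | 0.89-0.95 (0.4-0.7) | 4.6-7.4% |
| None at Week 12, correlation 0.8 | not listed | 10.7% |
| Re-dosed at first visit with WOMAC A sum ≥6 (about 75% at Week 12), 12-week correlation 0.32 / 0.44 / 0.51 / 0.61, contrast centred at zero | 0.76-0.89 | 8.0 / 10.6 / 11.3 / 9.9-13.3% |
| 120 pairs, 20 sites, range of settings | 0.76-1.00 | 5.4-16.4% |
| AUE, second-dose baseline | 0.90 | 8.2% |
| AUE, both changes from Day 1 | 0.98 | 4.8% |

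On comparable equal-mean data, a plain paired t-test rejected 3.8-6.6%, and REML with an unstructured 2x2 covariance rejected 3.5-6.2%. The type 3 patient variance was negative in at most 2% of trials, in one setting, so the handling of negative estimates does not explain the result.

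**Day 1 score in both rows.** Then B = 0, `base` drops out of the contrast, and the model reduces to a paired t-test: 4.8-5.0%.

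**Shift in the estimate.** Re-dosing depends partly on the second-dose-visit score (protocol 7.4.3.1). With an identical drug effect after each dose, one setting gave mean baselines of 2.38 and 1.76 and mean changes of −0.81 and −0.17. The raw paired difference is 0.81 − 0.17 = 0.64 points with no difference in the drug. In a separate set of runs, the mean shift was 0.02-0.16 with the printed code and 0.03-0.22 with REML/unstructured. In a further set, at correlation 0.5 and a 12-week effect of 0.4, the two rejected 18% and 27%.

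**The case against.** The code is offered as a sample, and the prose asks for a paired t-test. The study is single-arm and open-label with a safety objective. Efficacy is exploratory and unadjusted for multiplicity, and no decision is tied to this p-value. All of that stands, and it limits the severity. It does not remove the point, because no other code is given and the intervals and p-values will be reported.

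Four stronger readings are tempting, and the material does not support them:
- **That the SAP carries an 8-13% error rate.** That range depends on correlations and a Week 12 share that the documents do not give.
- **That every first-versus-second-dose result is affected.** Versions referenced to Day 1 are planned in 4.9.1.2 and 4.9.1.4, and 4.9.1.2 also shows the doses side by side from separate repeated-measures models.
- **That the score shared at Week 12 is the whole cause.** With nobody re-dosed at Week 12, rejection was still 7.6-8.2% at correlations of 0.5-0.7 in the 120-pair runs.
- **That changing two lines of code is a full repair.** With score-dependent re-dosing and the contrast centred at zero, REML/unstructured still rejected 6.7% and 8.3% (correlations 0.4 and 0.6), against 5.3% and 5.7% for the paired t-test. It does not remove the shift.

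**Conclusion.** The specification is wrong as written for the comparisons that use the second-dose-visit score as covariate. The standard error is usually too small, with ratios to the true value of roughly 0.76-0.95 in most settings tried. A nominal 5% test then rejects about 5% to 19% of the time over assumed correlations of 0.2-0.8, and typically 8-13% at mid-range correlations. The direction follows from the algebra. The size rests on assumed correlations, SD, drug-effect curve and Week 12 share.

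These rates take the model's own dose contrast as zero. If the null is instead an identical drug effect after each dose, the shift in the estimate adds to them, so 19% is not a worst case. Comparisons with Day 1 as reference and covariate in both rows have correct error bars. They remain uncontrolled before-and-after comparisons. Severity is SHOULD.

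**What to change.** 1. In the 4.9.1.2 code, and where 4.9.1.4 reuses it, replace `method=type3` with `method=reml` and `random subjID` with `repeated arm / subject=subjID type=un`, which is the structure 4.9.1.1 already uses. Report the plain paired t-test named in the text beside it.
2. In the Day 1-referenced comparison already planned in 4.9.1.2, state that the Day 1 score is the covariate in both rows, so that it reduces to a paired t-test. Make it the lead first-versus-second-dose comparison.
3. State that the comparison using the second-dose-visit baseline is descriptive, because patients are re-dosed partly on that score and neither REML/unstructured nor the paired t-test removes the resulting shift.

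Cost: two lines of code, a few sentences, one more table row, and somewhat wider confidence intervals. No new data are needed.

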##### **7.4.3.1. Repeat Administration Inclusion Criteria**

To be eligible to receive a repeat administration, patients must fulfill the following criteria:

1. Benefit from the initial dose of FX006 in the opinion of both the patient and the Investigator
2. No major safety concerns during the initial dose period as assessed by the Investigator
3. Clinically indicated to receive a second dose of FX006 in the opinion of both the patient and the Investigator
4. WOMAC A total sum score of  $\geq 6$  or a clinical rationale as to why a second dose is indicated
5. Compliant with study procedures and visit schedules through at least Week 12 and the willingness and ability to continue to comply through Week 52
6. Willingness to abstain from use of protocol-restricted medications during the study

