#### **4.2.8. Missing, Unused, and Spurious Data**

For WOMAC, the rules as described in the WOMAC user guide (Bellamy 2011) will be used. Specifically, if at least 2 pain, both stiffness, or at least 4 function items are missing, the patient's response will be regarded as invalid and the score for that given subscale as well as the total score will be left missing. If no more than 1 pain, 1 stiffness, and less than 4 function items are missing, the missing value in a given subscale will be imputed using the average of all items in the given subscale. Imputed WOMAC scores will be flagged in the data listings.

---

 Copyright 2015, SAS Institute Inc. SAS and all other SAS Institute Inc. product or service names are registered trademarks or trademarks of SAS Institute Inc., Cary, NC, USA.

For the KOOS QOL subscale, the rules as described in KOOS Scoring 2012 (<http://www.koos.nu/>) will be used. Specifically, the score is only calculated if at least 2 items are non-missing. Otherwise the score will be set to missing.

For calculating weekly mean steps per day using Fitbit data, patients need to have at least 3 of 7 daily values in a given week to provide a robust assessment of activity. The denominator used for calculating means will be the total number of days in which steps per day is non-missing.

To be included in the GPAQ analyses, there must be a valid response for at least one domain and no invalid responses for any domains.

Other than for the WOMAC and KOOS QOL, missing data will not be imputed and will be analyzed "as observed".

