**4.2.10.      Baseline Definitions**

Baseline for the first dose is the baseline/Day 1 assessment prior to administration of the first dose of study treatment. If the baseline result is missing, the last non-missing result prior to administration of study treatment may be used from the Screening period.

Baseline for the second dose of study treatment is defined as the last data collected prior to the second dose of study treatment administration. This is the same study visit, as long as the data are collected prior to the second dose.

Where noted in this SAP, change from baseline for efficacy analyses are also performed where baseline for the second dose is defined as the baseline/Day 1 assessment prior to administration of the first dose of study treatment.

Additional baselines may be defined to explore efficacy endpoints comparing the first dose and the second dose of study treatment administration. All new baseline definitions will be fully specified and documented in an interim SAP (iSAP) and in the final CSR.

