### 4.9.1. WOMAC

The following WOMAC scales/questions will be analyzed:

- WOMAC A (pain subscale)
- WOMAC B (stiffness subscale)
- WOMAC C (function subscale)
- WOMAC (total)

For the WOMAC subscales, scores at each assessment time point (baseline, Week 4, Week 8, Week 12, etc.) will be calculated as the average of the responses to all questions in the subscale. Total score will be computed as the average of the average responses on each of the subscales (e.g. Average A + Average B + Average C divided by 3). This will provide a uniform scoring of 0 to 4 for each subscale and easier interpretation. Imputation rules are as presented in section 4.2.8.

Eligibility in this trial is based upon the WOMAC A total sum score at Screening and Day 1/baseline (maximum score of 20). This will be provided for all visits in a data listing.

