A second analysis will be completed for patients who receive two doses of FX006. Change in WOMAC A, WOMAC B, WOMAC C and WOMAC total from first dose (Day 1) to Week 4, Week 8 and Week 12 will be presented alongside change in WOMAC from second dose to 4, 8 and 12 weeks after the second dose.

This will be done using a longitudinal MMRM as described in section 4.9.1.1 with fixed effects for study time point (Week 4, Week 8 and Week 12), study site and baseline score. Patient will be the random effect. The analysis will include all study visits of data (Week 4, 8 and 12) through Week 12. This model assumes that missing values are missing at random. Separate models will be run for the first and second doses.

This model will be run using the SAS/STAT® PROC MIXED procedure with an unstructured correlation matrix to model the within-subject errors. If the unstructured covariance matrix does not converge when fitting the mixed model, further investigation into the most appropriate

correlation matrix will be conducted. The final selection of the correlation matrix to be used in fitting the mixed model will be fully documented in the results section of the clinical study report.

This model will provide the adjusted LSM estimates at each visit with the corresponding standard error and associated 95% confidence interval.

In addition to change from baseline, descriptive statistics for the unadjusted observed WOMAC values will also be tabulated.

The same analysis that is described above for change from baseline will also be performed for percent change from baseline. Percent change from baseline will be calculated as follows:

$$\text{Percent change from BL} = (\text{Value} - \text{BL value})/\text{BL value} * 100$$

Line plots presenting observed, LSM change and LSM percent change from baseline in WOMAC A, WOMAC B, WOMAC C and WOMAC total score over time will be produced. In these plots, Week 4, Week 8 and Week 12 as well as 4, 8 and 12 weeks after the second dose, will be presented. There will be a separate line for the first and second dose along with standard deviation bars for observed values and standard error bars for adjusted values. LSM change from baseline and percent change from baseline will come from separate mixed models as described above.

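### The WOMAC percent-change MMRM has no floor under its denominator: zero baselines drop out and low ones inflate the variance

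*SAP*

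**What the plan says.** **The analysis.** SAP 4.9.1.2, under the Week 4, 8 and 12 analysis for two-dose patients, specifies an MMRM of change from baseline for WOMAC A, B, C and total. It then adds: "The same analysis that is described above for change from baseline will also be performed for percent change from baseline". The formula is (Value - BL)/BL × 100. On the model structure it says: "Separate models will be run for the first and second doses". Least-squares mean percent change is plotted with one line per dose.

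**The denominator.** SAP 4.2.10: "Baseline for the second dose of study treatment is defined as the last data collected prior to the second dose of study treatment administration". The last paragraph of SAP 4.9.1.2 repeats the analysis with Day 1 as the starting point for both doses. It names change and does not mention percent change, but the natural reading is that percent change is included.

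**The range of scores.** SAP 4.9.1 averages the items in each subscale: "This will provide a uniform scoring of 0 to 4 for each subscale and easier interpretation". Zero is therefore attainable.

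**The floors.** Protocol 7.4.2.1, criterion 7, requires a WOMAC A sum of at least 6 at Screening and at Day 1. It sets no minimum for stiffness or function. At re-dosing, Protocol 7.4.3.1, criterion 4, accepts a WOMAC A sum of at least 6 "or a clinical rationale as to why a second dose is indicated".

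**Missing values.** SAP 4.2.8 gives item-level rules for WOMAC. Neither document says what happens to percent change when the baseline is zero.

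**The concern.** Three features of the ratio cause trouble when the denominator is small.

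- **Zero baseline.** Percent change is undefined at every visit, so the patient contributes nothing to that model. On WOMAC such a patient can only stay at 0 or worsen, so the exclusion runs in one direction. The absolute-change and percent-change results in the same section then describe different patients.
- **Asymmetry.** Improvement cannot pass -100%, but worsening from a low start can reach several hundred percent.
- **Variance.** The spread of the ratio grows as the baseline falls, while the MMRM assumes normal errors with a common covariance matrix.

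The first and second effects push opposite ways. Dropping zeros makes the remaining patients look better, and low non-zero baselines make the mean look worse. The reader of the plot could not tell how much of either is present. Low denominators are more plausible at the second dose, because Protocol 7.4.3.1, criterion 1, requires benefit from the first. For stiffness and function, though, the gap exists at both doses.

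**Working it through.** **Sample size used.** The plan gives no figure for this analysis. Its only design calculation (SAP 4.1) reproduces: 200 × 0.66 × 0.75 = 99, against a target of 100. From it I take n = 200 × 0.66 = 132 two-dose patients. SAP Section 5 reports more than 90% re-dosed and about 10 patients with one dose, so about 180 to 190 if 200 were enrolled. I also use n = 190.

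**What the formula allows.**
- WOMAC A (five items, sum 0 to 20): 1 to 6 is +500%, 1 to 10 is +900%, 1 to 20 is +1900%.
- WOMAC B (two items, sum 0 to 8): 1 to 4 is +300%, 1 to 8 is +700%.
- WOMAC A with a baseline of at least 6: at most (20 - 6)/6 = +233%.
- WOMAC total on Day 1: at least (6/5)/3 = 1.2/3 = 0.4, so never zero. Its ceiling is (4 - 0.4)/0.4 = +900%, reached only from zero stiffness and function at entry.

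**One patient.** Assume the other n - 1 patients have mean -50% and SD 40 points. For a patient at x, let d = x + 50. The mean shifts by d/n. The SE without the patient is 40/√(n - 1), which is 3.5 at n = 132 and 2.9 at n = 190. The share of the total sum of squares is S/[(n - 2) × 40² + S], with S = d²(n - 1)/n.

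Example, x = +300%, n = 132: shift 350/132 = 2.7; S = 122,500 × 131/132 = 121,572; share 121,572/(208,000 + 121,572) = 37%.

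| Patient | Shift, n=132 | In SEs | Share of SS | Shift, n=190 | Share of SS |
|---|---|---|---|---|---|
| B 1 to 4 (+300%) | 2.7 | 0.8 | 37% | 1.8 | 29% |
| A 1 to 6 (+500%) | 4.2 | 1.2 | 59% | 2.9 | 50% |
| B 1 to 8 (+700%) | 5.7 | 1.6 | 73% | 3.9 | 65% |
| A 1 to 10 (+900%) | 7.2 | 2.1 | 81% | 5.0 | 75% |
| A 1 to 20 (+1900%) | 14.8 | 4.2 | 95% | 10.3 | 93% |
| A 6 to 20 (+233%) | 2.1 | 0.6 | 28% | 1.5 | 21% |

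**Several low WOMAC A baselines.** Simulation, n = 132. Assumed: baselines of 6 or more from a rounded normal (mean 9, SD 3, held to 6-20); lower ones spread evenly over 1-5, plus some zeros; follow-up = 2 + 0.35 × baseline + normal error (SD 3), rounded and held to 0-20.

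| Below 6 (of which 0) | Mean % | SD | Median % | Mean change / mean baseline, % | Mean change, points | Dropped |
|---|---|---|---|---|---|---|
| 0% (0%) | -40.9 | 35.2 | -43.5 | -42.7 | -3.95 | 0 |
| 5% (0%) | -36.8 | 49.5 | -42.7 | -41.8 | -3.74 | 0 |
| 10% (2%) | -34.1 | 57.8 | -42.2 | -40.6 | -3.49 | 2.6 |
| 20% (5%) | -28.2 | 72.0 | -40.7 | -38.1 | -3.00 | 6.6 |
| 30% (10%) | -23.1 | 82.2 | -39.3 | -34.7 | -2.46 | 13.2 |

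Not all of the move in the mean is artefact: patients starting lower also change less in points. From the first row to the last, mean percent change moves 17.8 points and the ratio of means 8.0. With 5% zeros, mean absolute change is -3.00 for everyone and -3.28 once the zeros are dropped.

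**Stiffness zeros.** Assume two 0-4 items, latent mean 1.4, 1.7 or 2.0, between-patient SD 0.75 and item SD 0.5. Both items are zero in 8.3%, 4.1% and 1.8% of patients, which at n = 132 is about 11, 5 and 2 patients dropped.

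These are simple means, not MMRM fits. The model's linear baseline term would absorb part of the pattern, but a 1/BL relation is not linear.

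**The case against.** The strongest reply is that little depends on this output. Efficacy is exploratory, the primary objective is safety, the two doses are modelled separately with no between-dose test of percent change, and absolute change and observed values stand in the same section. The Day 1 version already planned supplies a floor for WOMAC A. All of this stands and keeps the point minor. It does not remove the gap, since the Day 1 version gives no floor for stiffness or function.

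Three stronger readings are tempting, and the documents do not support them:

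- **That single patients dominate the mean.** At n = 132 to 190 most cases above move it by about two SE or less; only the extreme 1-to-20 case goes well beyond. What one patient can dominate is the SD and SE.
- **That excluded patients can only worsen.** They can also stay at 0. The exact statement is that they cannot improve.
- **That zero or near-zero baselines will occur in number.** The documents give no WOMAC means, SDs or counts below 6. They permit such baselines and say nothing about frequency. With none below 6, WOMAC A is unaffected.

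It would also be too narrow to blame the second-dose baseline alone, and too broad to discard the total score on the Day 1 baseline, which cannot be zero.

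**Conclusion.** The point holds as a minor one. The percent-change MMRM uses denominators that can be zero or near zero for stiffness and function at both doses, and for WOMAC A at the second-dose visit. The total at that visit can be zero only if all three subscales are. The plan has no rule for this.

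The consequences are a one-directional loss of patients who cannot improve, an inflated SD and SE, and, when several low baselines occur, a mean pulled towards less improvement. In the assumed scenarios the SD rises from 35 to 82 and the mean moves from -40.9% to -23.1%, while the median moves only from -43.5% to -39.3%.

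These sizes rest on assumed score distributions. Only the bounds and the floors come from the documents.

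If KOOS QOL is also given a percent-change model (SAP 4.9.2 refers back to this section), its zero is the worst score. The exclusion would then run the other way and remove patients who cannot worsen.

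**What to change.** In SAP 4.9.1.2:

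1. Keep the percent-change model on the Day 1 denominator for both doses for WOMAC A, where it lies between -100% and +233%. State explicitly that the Day 1 version includes percent change.
2. If wanted, keep WOMAC total on the same denominator (at least 0.4), noting its looser upper limit of +900%.
3. Drop the percent-change MMRM that uses the second-dose-visit baseline, and those for stiffness and function at either dose. Alternatively, replace them with the median percent change or the ratio of mean change to mean baseline.
4. Wherever a percent change is reported, state how a zero baseline is handled and give the number of such patients.
5. Leave absolute change as planned for all scales and both baselines. Say whether percent change applies to KOOS QOL and, if so, apply item 4.

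The cost is fewer exploratory percent-change outputs. No new data are needed.
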